Study Protocol with Statistical Analysis Plan

Study Title: Augmenting Exposure Therapy for Social Anxiety With Transcranial Direct Current Stimulation

NCT03743571

Document Date: Submitted to the IRB on March 26, 2020

Part II Application – Social Behavioral/Education Research

Note the following:

1. A Part I Cover sheet is required for each project submitted in IRBNet; see [Locating the Cover Sheet](#)
2. See IRB policy for submission requirements for new projects for [Full Committee Review](#) or [Expedited Review](#).

PI Responsibilities

1. How will the PI ensure that all study personnel are informed about the research plan and their research-related duties?	 Routine meetings  Regular communication (e.g., email, phone)  Other research staff training, describe:
--	--

Study Sites and Collaborating IRBS

2. List/describe the study sites:	UNR campus only
3. Will this research be reviewed by other IRBs?	 No  Yes (Consider contacting our office for assessment and coordination of single IRB review.)

Selection of Research Participants

4. How many participants (or records) will be enrolled?	200 Number of participants (NOTE: This is for participants enrolled in the in-person portion of the study. However, we expect that many of those who complete the online prescreen may not meet criteria for participating in the full/in-person study or may not wish to schedule in-person lab visits. We therefore expect the number of individuals who complete the online prescreen will be much higher than 200.)
5. What are the participant eligibility inclusion criteria?	

Inclusion criteria:

- 1) Age 18 or older (i.e., adult able to provide consent).
- 2) Identifies as Latino, or non-Latino and Caucasian
- 3) NOT currently receiving in exposure therapy for social anxiety.
- 4) Levels of social anxiety that are sufficiently high, defined as:
 - Reporting a 6 or higher in response to the question "How anxious would you feel giving a formal speech before a live audience?" on a 0 (no anxiety) to 8 (extreme anxiety) scale
 - Reporting a 5 or higher in response to the question "How likely would you be to avoid taking a class that required an oral presentation?" on a 0 (never avoid) to 8 (always avoid) scale

Age, specify: 18 or older

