---	---

28. State the study purpose, research hypothesis, or research questions:
	
Design: We will recruit participants with a fear of public speaking, the most commonly feared situation among individuals with social anxiety and among the general population [12-14]. Participants will be randomized to receive either active/anodal or sham tDCS stimulation targeting the vmPFC during one, 20 to 30-minute exposure therapy session delivered through virtual reality (VR). VR-based exposure therapy for public speaking anxiety is equally effective as in vivo/in life exposure therapy [8], but allows for greater consistency of the exposure environment between participants (e.g., consistency in listener facial expressions). During exposure therapy, participants will complete six, 3-minute public speaking trials. During each 3-minute public speaking trial, the audience will be comprised of either 75% Latino individuals/25% non-Latino Caucasian individuals, or 75% non-Latino Caucasian individuals/25% Latino individuals (gender of audience members will be equally distributed among each ethnicity group). Order of ethnicity matched and unmatched trials will be randomized.
 
Severity of social anxiety will be assessed at baseline and 1-month follow up with (1) a validated battery of questionnaires (the Personal Report of Public Speaking Anxiety and the Self-Statements during Public Speaking Scale), and (2) two behavioral approach tests (BATs), each involving a short speech in virtual reality to either an ethnicity matched or ethnicity unmatched audience. Fear will be assessed during each BAT behaviorally (total duration of speech out of a 5-min maximum), physiologically (electrodermal response and heart rate variability), and subjectively (peak fear rating on a scale from 0 to 100).
 
Study Aims:
 
Test the hypothesis that augmenting exposure therapy with tDCS facilitates alleviation of social anxiety symptoms. If tDCS targeting the mPFC improves treatment response, we would expect to detect lower symptom scores in the active (versus sham) tDCS group on self-report and BAT measures at 1-month follow-up. If tDCS is ineffective, we anticipate observing no differences in symptom severity between the active and sham tDCS groups at one-month follow-up.
 
Test the hypothesis that pairing exposure therapy with active (vs sham) tDCS facilitates extinction of fear response toward ethnic out-group, public speaking audiences. If tDCS facilitates reduction of fear toward ethnic out-group individuals, we expect an interaction between tDCS group (active vs. sham; between-subjects variable) and public speaking audience (ethnic-matched vs. ethnic-unmatched; within subjects variable) on behavioral, physiological, and subjective indices of fear response during the BATs at one-month follow-up. We expect that the active tDCS group will show equally low fear response on ethnic-matched and ethnic un-matched BATs at one-month follow-up, and the sham tDCS group will show higher fear responding during the ethnic un-matched BAT relative to the ethnic-matched BAT at one-month follow-up.

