30. Check all research methods/procedures that apply to this research:	
 Psychological or behavioral interventions/treatments
 
 Educational activities/interventions
 
 Experimental-control group assignment
 
 Cross-over design
 
 Computerized simulations
 
 Equipment/devices^{xi}, specify: transcranial direct current stimulation; Empatica E4, ambulatory physiological recording; HTC Vive (virtual reality)
 
 Ethnographic research
 
 Needs assessment research
 
 Program evaluation research
 
 Observational research
 
 Surveys, interviews, focus groups
 
 Collection of data from records
 
 Retrospective
 
 Prospective
 
 Other, specify:

31. Which of these methods/procedures are experimental (i.e., conducted to evaluate safety/efficacy or other outcomes) ^{xii} ?	Augmenting this exposure therapy with tDCS stimulation targeting the mPFC is experimental.
32. Which of these methods/procedures are considered standard-of-care?	Using exposure-based therapy to treat social anxiety is standard of care.
33. Who will provide the standard treatment or care referenced above?	
 N/A, research does not include usual care/standard treatment
 
 Study team
 
 Participant's own health care provider
 
 Other, specify

34. Why is group assignment necessary, and how will participants be assigned to treatment/experimental or control groups?	
 N/A, research does not involve group assignment
 
Justification/description: We will use a blocked randomization procedure and a random numbers generator to determine random assignment. Random assignment is necessary to provide an empirical evaluation of whether active/anodal tDCS improves outcomes relative to a placebo condition (sham tDCS stimulation).

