	
Before and after exposure therapy, and before and after each behavioral avoidance test (BAT), participants will additionally self-report on their emotional state (e.g., fear levels) and beliefs (e.g., belief that public speaking practices will be/were harmful/negative). During exposure therapy, participant's physiological responding will be recorded (heart rate and electrodermal skin response). After exposure therapy is complete, participants will fill out a question indicating their best guess as to their treatment assignment (placebo or active tDCS). This question is to ensure that blinding was effective.
 
Behavioral avoidance tests (BATs): Participants will be complete two behavioral avoidance tests. The BATs will involve providing two public speeches to an audience in virtual reality that is A) 75% matched to the participant's ethnicity, and b) 75% un-matched to the participant's ethnicity. Participant's responding will be measured subjectively (with self report items), physiologically (with electrodermal skin response and with heart rate), and behaviorally (recording duration eye contact with audience members, and overall duration of the speech). The subjective, physiological, and behavioral measures of anxiety during the behavioral avoidance task provide a triangulated measurement of the construct of public speaking anxiety. The behavioral approach tests will be completed at baseline and 1-month follow up.
 
Modifications to procedures due to COVID-19 restrictions: For the online follow-up survey, only the following questionnaires will be included, due to participants' completing the survey at home: Intergroup Anxiety Scale, Personal Report of Public Speaking Anxiety, Self-Statements During Public Speaking, and a modified MINI – Social Anxiety interview so that participants can answer the questions without the presence of an interviewer. See Appendix- Questionnaires to view interviews that have been modified to questionnaires.

40. How will researchers analyze the data? ^{xvi}	Primary analyses will be ANCOVAs, evaluating the impact of tDCS group (active vs sham) on outcome measures (questionnaires, physiology, and behavior) at post-treatment and follow-up, controlling for baseline levels. The hypothesis is that participants with active (vs sham) tDCS will have

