	
lower symptom scores at post-treatment and follow-up (adjusting for baseline levels).
 
We will also use a repeated-measures ANOVA to examine whether tDCS group (active vs sham; between-subjects variable) interacts with ethnic make-up of the public speaking audience (ethnicity- matched vs. ethnicity-unmatched; within-subjects variable) to determine fear response on each index of fear reactivity (behavioral, physiological, and subjective fear response) at one-month follow-up.

41. Will this research include records of participants' voices or images? ^{xvii}	
 No
 
 Yes, audio; describe and justify:
 
 Yes, video; describe and justify:
 
 Yes, photographs; describe and justify:

Research Risks	

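### Aim 2: with an uneven ethnic mix, match status is partly confounded with audience scene, because the two-factor ANOVA leaves out participant ethnicity

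*Combined protocol and SAP*

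**What the plan says.** Item 5 admits anyone who "Identifies as Latino, or non-Latino and Caucasian", and Item 4 gives the size as "200 Number of participants". No number or ratio per ethnic group appears.

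Item 28 describes two mirror-image audiences for the exposure trials: "the audience will be comprised of either 75% Latino individuals/25% non-Latino Caucasian individuals, or 75% non-Latino Caucasian individuals/25% Latino individuals". Aim 2 is measured on the behavioural approach tests (BATs), which Item 39 defines relative to the speaker: one audience "75% matched to the participant's ethnicity, and b) 75% un-matched to the participant's ethnicity". With two eligible groups, these imply the same two compositions. That the BATs show the same scenes as the exposure trials is an inference, not stated text.

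On comparability of the audiences, Item 28 says "gender of audience members will be equally distributed among each ethnicity group" and cites consistent listener expressions across participants as an advantage of VR. Nothing says that the two audiences were equated or pretested for how much fear they provoke. Item 28 also says "Order of ethnicity matched and unmatched trials will be randomized", which concerns the exposure trials; BAT order is not stated.

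Item 34 says "We will use a blocked randomization procedure and a random numbers generator to determine random assignment", with no stratum for ethnicity. Item 40 tests whether tDCS group ("active vs sham; between-subjects variable) interacts with ethnic make-up of the public speaking audience") at one month. Participant ethnicity and the baseline BATs are not in that model. Item 28 predicts that sham participants will be more fearful before the unmatched audience, and active participants equally calm before both.

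**The concern.** For a non-Latino participant the Latino-majority audience is the unmatched one. For a Latino participant it is the Caucasian-majority audience. Within each ethnic group, therefore, match status and audience scene are one and the same contrast. They separate only when the two groups are compared or given equal weight. Recruitment through the student pool, classes, flyers and social media (Items 3 and 10) gives no reason to expect an even split.

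At stake is how Aim 2 is interpreted. The result is meant to show whether tDCS reduces fear of the ethnic out-group. If one virtual audience is more intimidating for unrelated reasons, such as faces or realism, a reaction to that scene could be read as out-group fear, or could hide it.

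**Working it through.** The plan gives no power calculation, SD, effect size or alpha, so there is no figure to reproduce.

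**Inputs from the documents:** 200 participants, two mirror-image audiences, a 0-100 subjective fear scale, a two-factor ANOVA.

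**Assumptions:** 1:1 allocation with 100 per arm at follow-up; two-sided 5% test; residual SD of the within-person gap 15 points; scene effect A = 8 or 16 points in sham (Latino-majority minus Caucasian-majority audience); non-Latino share p = 0.50 to 0.85; no true match effect.

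**Model.** For each person, gap = unmatched minus matched fear = match effect + e × A, where e = +1 for non-Latino and −1 for Latino participants. The mean of e is 2p − 1. With no match effect, the mean gap in an arm is (2p − 1)A and its variance is [15² + 4p(1 − p)A²]/100. The group-by-match test compares mean gaps between arms.

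**Case 1: same scene effect in both arms.** Interaction bias = (2p − 1)(A − A) = 0. The rejection rate is 5.0% at every p. A simulation with 20,000 trials per setting and scene effects of 0.3 and 0.5 SD gave 4.9-5.1% for p from 0.5 to 0.9.

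**Case 2: the sham contrast alone.** Bias = (2p − 1)A, whatever tDCS does. At A = 8 and p = 0.75, bias = 0.5 × 8 = 4.0 points, SE = √[(225 + 0.75 × 64)/100] = 1.65, and the ratio is 2.4, so a false finding is more likely than not (about 68%). In the simulation, the false-positive rates were:

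| Scene effect | p = 0.6 | 0.7 | 0.8 | 0.9 |
|---|---|---|---|---|
| 0.3 SD | 9% | 21% | 41% | 65% |
| 0.5 SD | 15% | 43% | 79% | 96% |

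**Case 3: tDCS shrinks the scene effect from A to B.** Interaction bias (sham minus active) = (2p − 1)(A − B). Its variance is the sum of the two arm variances. Example: A = 8, B = 4, p = 0.75 gives bias 0.5 × 4 = 2.0; SE = √[(225 + 0.75 × 64)/100 + (225 + 0.75 × 16)/100] = √5.10 = 2.26; rejection rate 14%.

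| Scene effect, sham → active | p = 0.65 | 0.75 | 0.85 |
|---|---|---|---|
| 8 → 6.4 (20% cut) | 5.5% | 6.4% | 7.9% |
| 16 → 12.8 (20% cut) | 6.3% | 8.9% | 14% |
| 8 → 4 (halved) | 8% | 14% | 24% |
| 16 → 8 (halved) | 14% | 33% | 62% |

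At p = 0.50 every row is 5%.

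**Direction.** The bias mimics the prediction when the scene the majority group finds unmatched is also the more feared one. Otherwise its sign reverses. By symmetry, a mostly Latino sample (p below 0.5) behaves the same way with the signs exchanged.

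**Fewer follow-up BATs.** At an assumed 60 per arm, the halved figures at p = 0.75 fall from 14% to 10.5% and from 33% to 22%.

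**Equal-weight analysis.** Averaging the group-specific gaps gives [(match + A) + (match − A)]/2 = match, so the scene effect drops out. With a scene effect present only in sham, simulated bias was about 0 and the false-positive rate 4.3-5.5% for p from 0.5 to 0.9.

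**The case against.** The strongest reply is that randomisation already protects Aim 2. tDCS is allocated between participants, everyone is meant to do both BATs, and the stated test is the interaction. A scene difference common to both arms cancels in expectation. This is correct. A reader might infer from the swapped labels that a scene difference alone can produce the predicted interaction; the design does not allow that, as Case 1 shows. Chance ethnic imbalance between arms (SD about 6 to 7 percentage points) can move a single estimate but does not inflate the error rate.

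It can also be said that the larger rates need three assumptions at once: a 16-point scene gap, a strongly skewed mix, and a single session that halves the scene effect at one month. The documents support none of these. That stands, and it is why the 20% rows belong beside the halved ones. Nor would a uniform drop in fear be enough, since it leaves the scene gap intact; the reduction must be larger where fear is higher. Item 28 does predict lower BAT fear under active tDCS, so such a reduction is plausible, but it is not established.

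The direction is also open, and Item 39 limits the online follow-up during campus closure to questionnaires, so some participants may have no follow-up BAT.

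What survives is that the sham contrast, half of the predicted pattern, has no protection from randomisation, and that the interaction is protected only if tDCS leaves the scene difference unchanged.

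**Conclusion.** The concern holds in a limited form. In the available text nothing fixes the ethnic mix, and the Aim 2 model cannot separate match from scene when the mix is uneven. The sham contrast is biased by (2p − 1) × the scene effect. The interaction is biased by (2p − 1) × the change in scene effect under tDCS, and is unbiased if that change is zero or the mix is even. Under the assumptions listed, the interaction's false-positive rate is about 5.5-14% for a 20% reduction and 8-62% for a halving.

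The documents do not support saying that Aim 2 is invalid, or that its interaction test is inflated as a matter of course. The actual mix, the scene effect and the effect of tDCS on it are all unknown. This is a cheap improvement to the analysis rather than a fatal flaw.

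**What to change.** Amend Item 40. Add participant ethnicity and its interactions with tDCS group and match to the Aim 2 model. Estimate both the tDCS-by-match interaction and the sham matched-versus-unmatched contrast with equal weight on the two ethnic groups. Report the scene difference from the baseline BATs, estimated as half the difference between the non-Latino and Latino mean gaps. This rests on the scene effect being similar in the two groups, which should be stated.

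No new data are needed: ethnicity is an eligibility criterion and the baseline BATs are already planned. It also works for participants already randomised.

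The cost is precision. For a given residual SD, equal weighting multiplies the standard error by √[0.25(1/p + 1/(1 − p))]: 1.05 at 65/35, 1.155 at 75/25 and 1.40 at 85/15. Removing scene variance from the residual offsets part of this. For example, with an 8-point scene effect in both arms at 75/25, the SE is 2.45 (√4.5 × 1.155) against 2.34 (√5.46) for the stated analysis.

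Recruiting the remaining participants towards an even split would reduce both the bias and this cost, but may slow enrolment. Stratifying the remaining randomisation by ethnicity is optional. It limits chance imbalance between arms and does not remove this bias, which arises even when both arms have the same mix.

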30. Check all research methods/procedures that apply to this research:	
 Psychological or behavioral interventions/treatments
 
 Educational activities/interventions
 
 Experimental-control group assignment
 
 Cross-over design
 
 Computerized simulations
 
 Equipment/devices^{xi}, specify: transcranial direct current stimulation; Empatica E4, ambulatory physiological recording; HTC Vive (virtual reality)
 
 Ethnographic research
 
 Needs assessment research
 
 Program evaluation research
 
 Observational research
 
 Surveys, interviews, focus groups
 
 Collection of data from records
 
 Retrospective
 
 Prospective
 
 Other, specify:

31. Which of these methods/procedures are experimental (i.e., conducted to evaluate safety/efficacy or other outcomes) ^{xii} ?	Augmenting this exposure therapy with tDCS stimulation targeting the mPFC is experimental.
32. Which of these methods/procedures are considered standard-of-care?	Using exposure-based therapy to treat social anxiety is standard of care.
33. Who will provide the standard treatment or care referenced above?	
 N/A, research does not include usual care/standard treatment
 
 Study team
 
 Participant's own health care provider
 
 Other, specify

34. Why is group assignment necessary, and how will participants be assigned to treatment/experimental or control groups?	
 N/A, research does not involve group assignment
 
Justification/description: We will use a blocked randomization procedure and a random numbers generator to determine random assignment. Random assignment is necessary to provide an empirical evaluation of whether active/anodal tDCS improves outcomes relative to a placebo condition (sham tDCS stimulation).

35. What will participants experience or be asked to do when assigned to the treatment / experimental group or to the control group?	All participants will complete one session of exposure therapy for public speaking (six, 3-minute trials of exposure therapy). During exposure therapy, they will be engaging in public speaking in a VR-based environment. All participants will complete six, 3-minute public speaking trials, each of which will be with an 75%-ethnicity matched or 75%-ethnicity unmatched public speaking audience (order of trials will be randomized).

Treatment-group specific tasks: During their public speaking exposure therapy, participants will receive either (a) active or (b) sham tDCS stimulation. In the active and sham tDCS stimulation groups, anodal tDCS will be applied to target the vmPFC (Hammerer et al., 2016). Participants in the active tDCS group will receive 2 mA anodal stimulation during the exposure therapy task, and participants in the sham group will receive sham tDCS stimulation for about 20-30 s at the beginning and ending of the task to mimic the sensation of active tDCS (Zhao et al., 2017).

Additional information on tDCS procedures:

The tDCS administration procedures will include the following steps:

- (1) The participant's head is measured for appropriate placement of the electrodes (following the 10-20 international EEG convention). A towel is draped over the participant to prevent any saline drips from the electrodes.
- (2) The 5 x 5 cm or 5 x 7 cm saline dampened electrodes are then placed on the participant's head and held in place with adjustable bands. Electrodes may be placed on a single cortical area and a ground site (e.g. right parietal, left cheek or orbitofrontal region), or on two cortical sites (e.g. right parietal, right frontal).
- (3) If it is an anodal session, tDCS stimulation is applied approximately 20-30 minutes at 2 mA. Stimulation ends at the programmed time. During sham sessions, the electrodes are attached, and a low current is supplied for approximately the first and last 20-30 seconds to mimic the anodal tDCS experience. Electrodes are removed at the end of stimulation. Stimulation is perceived by most people only at the onset and offset of stimulation. Participants describe the sensation as a slight tingling sensation. In most participants, there is no abnormal sensation during the bulk of the stimulation period.

The experimenter directly administering the tDCS will be blind to the treatment condition (i.e., placebo vs active tDCS).

	
Reports, 6, 25160.
 

36. Note the expected number/length of contacts/meetings, and time commitment for participation (include similar information in consent materials):	
2 Expected number of contacts/meetings 60-120 min Minutes/hours for each contact/meeting (estimated) 1 visit Duration of participation (in weeks/months) for intervention 1 month Duration of participation (in weeks/months) for long-term follow-up

Data Collection and Analysis	
37. List the information/specimens that researchers will obtain for this research ^{xiii} :	
Researchers will collect questionnaire and interview data related to social anxiety severity and potential moderators of treatment (see research instrument section), physiological data (skin conductance and heart rate) to assess for increases in anxiety, and behavioral data (behavioral performance measured in total duration of public speeches; and in total duration of eye contact with audience members as recoded by the VR program).

38. How will research data be obtained? ^{xiv}	
Questionnaire/self-report and interview data will be collected in the laboratory. Participants will fill out questionnaires via Qualtrics. Research staff will administer the interviews and record responses in Qualtrics.
 
Modifications to procedures due to COVID-19 restrictions: “In the case of campus closure, follow-up self-report data will be collected via an online survey. Participants will be emailed one-month after their first visit. The email will include a description of the modified procedures (i.e., online survey rather than in-person visit due to campus closure; reduced gift card compensation amount) and a link to the Qualtrics survey. Participants’ emails will be linked to the survey so that researchers can view when the survey has been completed and provide compensation. Reminder emails will be sent after the first email if the participants have not completed the surveys.
 
Physiological data (skin conductance and heart rate) will be collected via an Empatica E4 wristband during behavioral avoidance tests.

	
Behavioral performance (e.g., speech duration) will be coded by research staff and by the output from the virtual reality program. Eye contact duration with audience members will be recorded via the virtual reality program. This information is labeled with time/date and will be stored in a study folder in Nevada box, labeled with the participant ID number (not with any identifying information).


39. Identify each research instrument (e.g., diary, questionnaire, data collection log) and describe how its use relates to the study purpose^{xv}:
	
Participants will complete a demographics questionnaire at baseline, along with an inclusion/exclusion criteria screening interview.
 
Social Anxiety Questionnaires: Social Anxiety questionnaires include the Personal Report of Public Speaking Anxiety, the Self-Statements during Public Speaking Scale, and an interview for social anxiety disorder (the MINI International Neuropsychiatric Interview- Social anxiety section; see Appendix). Except for the interview, these are each Likert-style questionnaires that evaluate severity of social anxiety symptoms. These will be administered at baseline and one-month follow up.
 
We will provide additional questionnaires that are all potential treatment moderators. These include (a) a Color of My Skin Interview (because the participant's perception of their skin tone might moderate their response to public speaking audiences of different skin tones), (b) the intergroup contact questionnaire (because those with greater experience with the ethnic out-group may be less fearful when the audience is mostly ethnic out-group members), and (c) the intergroup anxiety scale (because those with lower intergroup anxiety may respond less fearfully when the audience is mostly ethnic out-group members).
 
Immediately after participants are told about the treatment, they will also complete a treatment Credibility and Expectancy Questionnaire.
 
After the VR and tDCS sessions we will also administer (a) the iGroup Presence Questionnaire (because participants who find the VR experience immersive rather than 'fake' may demonstrate better outcomes), and (b) a side effects questionnaire (for monitoring possible adverse effects of tDCS and VR).

	
Before and after exposure therapy, and before and after each behavioral avoidance test (BAT), participants will additionally self-report on their emotional state (e.g., fear levels) and beliefs (e.g., belief that public speaking practices will be/were harmful/negative). During exposure therapy, participant's physiological responding will be recorded (heart rate and electrodermal skin response). After exposure therapy is complete, participants will fill out a question indicating their best guess as to their treatment assignment (placebo or active tDCS). This question is to ensure that blinding was effective.
 
Behavioral avoidance tests (BATs): Participants will be complete two behavioral avoidance tests. The BATs will involve providing two public speeches to an audience in virtual reality that is A) 75% matched to the participant's ethnicity, and b) 75% un-matched to the participant's ethnicity. Participant's responding will be measured subjectively (with self report items), physiologically (with electrodermal skin response and with heart rate), and behaviorally (recording duration eye contact with audience members, and overall duration of the speech). The subjective, physiological, and behavioral measures of anxiety during the behavioral avoidance task provide a triangulated measurement of the construct of public speaking anxiety. The behavioral approach tests will be completed at baseline and 1-month follow up.
 
Modifications to procedures due to COVID-19 restrictions: For the online follow-up survey, only the following questionnaires will be included, due to participants' completing the survey at home: Intergroup Anxiety Scale, Personal Report of Public Speaking Anxiety, Self-Statements During Public Speaking, and a modified MINI – Social Anxiety interview so that participants can answer the questions without the presence of an interviewer. See Appendix- Questionnaires to view interviews that have been modified to questionnaires.

40. How will researchers analyze the data? ^{xvi}	Primary analyses will be ANCOVAs, evaluating the impact of tDCS group (active vs sham) on outcome measures (questionnaires, physiology, and behavior) at post-treatment and follow-up, controlling for baseline levels. The hypothesis is that participants with active (vs sham) tDCS will have

	
lower symptom scores at post-treatment and follow-up (adjusting for baseline levels).
 
We will also use a repeated-measures ANOVA to examine whether tDCS group (active vs sham; between-subjects variable) interacts with ethnic make-up of the public speaking audience (ethnicity- matched vs. ethnicity-unmatched; within-subjects variable) to determine fear response on each index of fear reactivity (behavioral, physiological, and subjective fear response) at one-month follow-up.

41. Will this research include records of participants' voices or images? ^{xvii}	
 No
 
 Yes, audio; describe and justify:
 
 Yes, video; describe and justify:
 
 Yes, photographs; describe and justify:

Research Risks	
42. Describe how risks will be minimized through use of sound research design:	
 N/A, minimal risk research
 
Description:
 
1) One risk is breach of confidentiality because we are collecting identifying information (name, phone number, email address). This risk is minimized by linking identifying data to the primary study dataset (i.e., data collected during all in person visits) only through a hard copy, linking document, which will be stored separately from the rest of the research data. This linking document will be stored in a locked file cabinet in the laboratory. For the pre-screening assessment, however, identifying data will need to be collected along with eligibility information (pre screening assessments), so that researchers can contact eligible participants to set up appointment times. Only researchers who are IRB-approved (on this protocol) will have access to the pre-screening data set. Furthermore, we have tried to minimize any collection of identifiable private information on the prescreening form by categorizing all health-related conditions into one yes/no questions (so the participant does not need to identify any particular health condition they may have which would exclude them from the study, such as current pregnancy or a history of seizure or neurological condition).
 
2) A second risk relates to the use of tDCS. There is risk of seizure, skin irritation (itching, tingling, redness, pain) and burning associated with the application of electrical current to the scalp. There is risk of headache and discomfort from the adjustable bands that hold the electrodes in place. Seizure activity is associated with symptoms of attention deficiency, nausea, mood changes, and changes in perception, thus, these symptoms are also monitored.
 
However, to our knowledge, there have been no reported seizures associated with tDCS. Thus, symptoms associated with seizure activity (nausea, mood and perceptual changes) are unlikely. The stimulus parameters we propose are consistent with what has been safely used by other researchers and because of this we think that the likelihood of a serious event is very small.

	
Our best estimate of other more minor symptoms comes from a recent publication. Poreisz et al., (2007) tested 102 participants in 567 tDCS sessions. In post-session questionnaires asking for ratings from 1(low) - 5 (high), a mild-tingling sensation occurred in 71% of participants and was given a mean rating of $1.74 \pm .84$. Other effects included moderate fatigue in 35% (rated 2.17 ± 1.11), itching under the electrode placement in 30% (rated $1.6 \pm .72$). More serious symptoms of burning sensations were reported in 22% (rated $1.59 \pm .91$) and pain in 16% (rated $1.41 \pm .71$). However, no participant asked to terminate a session. In our testing experience, participants describe a slight itching sensation when the stimulation begins and ends. We anticipate participants describing slight itching and tingling. If participants report burning and pain at any point during the session, we will ask them if they would like to end the testing session. If the symptoms are not resolved by ending stimulation, we will take the participant to the health center or call medical emergency services if needed. If the participant reports feeling extreme symptoms during stimulation in the 'Post-Study Questionnaire' we will speak with the participant to see if medical attention is needed.
 
3) Additionally, completing procedures such as exposure therapy and the behavioral avoidance tests, can produce an increase in anxiety; during these procedures participants are engaging in a feared task on purpose (in this study, giving a public speech). However, this risk of psychological distress does not exceed what one might experience in daily life (e.g., when asked to provide a speech/presentation in a classroom setting). To provide participants resources for additional social anxiety treatment if desired, all participants who begin treatment will be provided a referral document, listing contacts for local mental health resources, at the end of the study.
 
4) Finally, the use of immersive virtual reality (used to administer exposure therapy in our study) can occasionally lead to transient side effects such as motion sickness, dizziness, or headaches. Following procedures used by prior studies of VR-based exposure therapy for public speaking anxiety (Anderson et al., 2013), we will mitigate the risk of simulator sickness by limiting the virtual reality exposure therapy session to 20-30 minutes. Participants will be allowed to request to stop VR sessions early, or take breaks during VR sessions, as needed if they are experiencing symptoms associated with simulator sickness.
 
Anderson, P. L., Price, M., Edwards, S. M., Obasaju, M. A., Schmertz, S. K., Zimand, E., & Calamaras, M. R. (2013). Virtual reality exposure therapy for social anxiety disorder: A randomized controlled trial. Journal of Consulting and Clinical Psychology, 81(5), 751-760. http://dx.doi.org/10.1037/a0033559
 

43. What precautions will researchers use to avoid unnecessarily	
Check all that apply:
 
 N/A, minimal risk research
 
 Using recognized standard practices
 
 Ensuring researcher expertise/credentialing

exposing participants to risk?
	
 Researcher training  Minimizing time required for procedures  Using procedures that are already being performed (e.g., for education or treatment) – use of the tDCS  Monitoring participants for adverse reactions  Monitoring data for safety  Other, specify:


44. List the discomforts and physical harms that might result from participation in this research; assess the probability, severity, and duration of each discomfort/harm:
	
1) Potential physical discomfort associated with tDCS: There is risk of seizure, skin irritation (itching, tingling, redness, pain) and burning associated with the application of electrical current to the scalp. There is risk of headache and discomfort from the adjustable bands that hold the electrodes in place. Seizure activity is associated with symptoms of attention deficiency, nausea, mood changes, and changes in perception, thus, these symptoms are also monitored. However, there have been no seizures associated with tDCS. Symptoms associated with seizure activity (nausea, mood and perceptual changes) are unlikely. The stimulus parameters we propose (1-2 mA stimulation) are consistent with what has been safely used by other researchers and because of this we think that the likelihood of a serious event is very small.
 
Our best estimate of other more minor symptoms comes from a publication on a large sample exposed to tDCS. Poreisz et al., (2007) tested 102 participants in 567 tDCS sessions. In post-session questionnaires asking for ratings from 1(low) - 5 (high), a mild-tingling sensation occurred in 71% of participants and was given a mean rating of $1.74 \pm .84$. Other effects included moderate fatigue in 35% (rated 2.17 ± 1.11), itching under the electrode placement in 30% (rated $1.6 \pm .72$). More serious symptoms of burning sensations were reported in 22% (rated $1.59 \pm .91$) and pain in 16% (rated $1.41 \pm .71$). However, no participant asked to terminate a session. In our testing experience (in the [name]/co-PI lab), participants typically describe a slight itching sensation when the stimulation begins and ends. Therefore, we anticipate participants will likely describe slight itching and tingling, but that this effect will be transient.
 
(2) Potential simulator sickness related to VR use: Probability of simulator sickness is reported by Gregg & Tarrier (2007): "In a series of experiments 80% of all participants reported an increase in sickness symptoms following immersions in a virtual environment (Cobb et al., 1999). For the majority this was a mild increase, which subsided after exiting the immersion. However, 5% could not complete the immersion because the effects were so aversive. Symptom onset typically occurred within 15 min of starting. In repeated trials, symptoms were worse during the first immersion and were negligible by the third."
 
Thus, it is likely that a participant might experience a mild, but transient, increase in simulator sickness symptoms (e.g., slight nausea, headache, etc), but rare that the increase would be so significant that a participant would need to terminate an exposure therapy session. This risk is further mitigated in the present study due to little to no movement in position during the public speaking simulation.
 

